#### **9.5. Events of Clinical Interest**

Not applicable.

#### **9.6. Emergency Unblinding of Treatment Assignment**

Not applicable.

## 9.7. Pregnancy

Pregnancy, in and of itself, is not regarded as an AE unless there is suspicion that the study drug may have interfered with the effectiveness of a contraceptive medication or method. When a pregnancy has been confirmed in a participant during maternal or paternal exposure to study drug, the following procedures should be followed in order to ensure safety:

- The study treatment must be interrupted immediately (female participants only).
- If the female participant is no longer pregnant and meets the treatment continuation criteria within 14 days of the scheduled start of a cycle, study treatment may be resumed after approval has been received from the sponsor medical monitor.
- The investigator must complete and submit the Incyte Clinical Trial Pregnancy Form to the sponsor or its designee within **24 hours** of learning of the pregnancy.

Data on fetal outcome are collected for regulatory reporting and drug safety evaluation. Follow-up should be conducted for each pregnancy to determine outcome, including spontaneous or voluntary termination, details of the birth, and the presence or absence of any birth defects, congenital abnormalities, or maternal and/or newborn complications, by following until the first well-baby visit. Pregnancy should be recorded on a Clinical Trial Pregnancy Form and reported by the investigator to the sponsor or its designee. Pregnancy follow-up information should be recorded on the same form and should include an assessment of the possible causal relationship to the sponsor's study drug to any pregnancy outcome, as well as follow-up to the first well-baby visit or the duration specified in local regulations, whichever is later. Refer to the Incyte Reference Guide for Completing the Clinical Trial Pregnancy Form or Study Reference Manual.

**Any SAE occurring during pregnancy of a study participant must be recorded on the Serious Adverse Event Report Form and submitted to the sponsor or its designee.**

Abnormal pregnancy outcomes (eg, spontaneous abortion, fetal death, stillbirth, congenital anomalies, or ectopic pregnancy) are considered SAEs (if occurring in the study participant) and must be reported as described in Section 9.4. If an abnormal pregnancy outcome is reported in a study participant's partner, the event should be reported to the sponsor on the Clinical Trial Pregnancy Form.

## 9.8. Warnings and Precautions

Special warnings or precautions for the study drug, derived from safety information collected by the sponsor or its designee, are presented in the IB. Additional safety information collected between IB updates will be communicated in the form of Investigator Notifications. Any important new safety information should be discussed with the participant during the study as necessary. If new significant risks are identified, they will be added to the ICF.

## 9.9. Product Complaints

The sponsor collects product complaints on study drugs and drug delivery systems used in clinical studies in order to ensure the safety of study participants, monitor quality, and facilitate process and product improvements.

All product complaints associated with material packaged, labeled, and released by the sponsor or its designee will be reported to the sponsor. All product complaints associated with other study material will be reported directly to the respective manufacturer.

The investigator or his/her designee is responsible for reporting a complete description of the product complaint via email or other written communication to the sponsor contact or respective manufacturer as noted in the packaging information. Any AE associated with a product complaint should be recorded as described in Section [9.3](#).

If the investigator is asked to return the product for investigation, he/she will return a copy of the product complaint communication with the product.

## **9.10. Treatment of Overdose**

There has been no clinical experience with overdose of pemigatinib. Treatment of overdose should consist of general supportive measures.

## 10. STATISTICS

### 10.1. Sample Size Determination

Approximately 125 participants with select FGFR alterations are planned for the final analysis of the endpoint of ORR. With the assumed rates of 40% for pemigatinib, a sample size of approximately 100 participants would provide about > 95% probability to have a 95% CI with lower limit of > 20%. Up to 25 participants will be enrolled in Cohort B, which will provide > 80% chance of observing at least 3 responders in this cohort if the underlying ORR is 20%.

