## **8.2. Efficacy Assessments**

### **8.2.1. Tumor Imaging**

Objective assessment of tumor status is required using appropriate disease-specific techniques, and a central radiologic facility will be used to determine responses and will be logged in to the eCRF. RECIST v1.1 ([Eisenhauer et al 2009](#)) will be used, and the recommended method for measuring and following tumor burden will be CT scan to include the thorax, abdomen, and pelvis; the neck and head may be included if clinically indicated. In cases where participants are diagnosed with brain metastases prior to initiation of study, standard-of-care brain scans would be clinically appropriate. Alternative modalities (eg, MRI) may be substituted for a CT scan at the discretion of the investigator, provided that the same modality is used throughout the study and that the methodology is consistent with RECIST v1.1.

The schedule for efficacy assessments will be at screening (this will be considered the baseline scan), every 9 weeks (ie, every 3 cycles starting at Cycle 3), and then at EOT (if applicable). If a participant discontinues before the first on-treatment assessment, and the baseline imaging was performed in the 2 weeks before Cycle 1 Day 1, then an EOT assessment is not required.

Imaging should continue in 9-week intervals regardless of delays in cycle starts. For participants showing a response, a confirmatory scan may be performed a minimum of 4 weeks (per RECIST v1.1) from the previous scan. For participants showing a progression based on local radiologic review, treatment should not be discontinued until progression of disease has been determined by the ICR group unless the principal investigator believes it is in the best interest of the participant to discontinue treatment before receiving confirmation.

For participants who discontinue treatment for reasons other than disease progression, every effort should be made to continue monitoring their disease status by radiographic imaging until the start of new anticancer therapy, documented disease progression, death, or the end of the study, whichever occurs first.

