**Table 13: Populations for Analysis**

Population	Description
Full analysis set	
The full analysis set includes all enrolled participants who received at least 1 dose of pemigatinib.
 
The full analysis set will be used for the summary of demographics, baseline characteristics, participants disposition, and analyses of all efficacy data,

Safety	
The safety population includes all enrolled participants who received at least 1 dose of pemigatinib.
 
All safety analyses will be conducted using the safety population.

Per protocol	Participants in the full analysis set who are considered to be sufficiently compliant with the Protocol comprise the per protocol population.
RECIST evaluable	The RECIST evaluable population includes all participants in full analysis set who have at least 2 objective tumor response assessments per ICR review or who withdrew from the study or discontinued treatment without post-treatment tumor assessments.

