## **10.5. Interim Analysis**

A futility analysis will be performed when approximately 25 participants are enrolled into Cohort A and have at least 2 objective tumor response assessments per ICR review or are withdrawn from the study or discontinued from treatment without post-treatment tumor assessments. Cohort A can be stopped for futility if  $\leq 6$  responders are observed in the RECIST evaluable population, for which there is  $< 15\%$  probability of claiming ORR  $> 20\%$  at final analysis. This rule is just a guidance and nonbinding.

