3.3. Sample Size Considerations

Approximately 125 participants with select FGFR alterations are planned for the final analysis of the primary endpoint of ORR. With the assumed rates of 40% for pemigatinib, a sample size of approximately 100 participants would provide about > 95% probability of having a 95% CI with a lower limit of > 20%.

Up to 25 participants will be enrolled in Cohort B, which will provide > 80% chance of observing at least 3 responders in this cohort if the underlying ORR is 20%.

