5. STATISTICAL METHODOLOGY

5.1. General Methodology

Unless otherwise noted, SAS® software (SAS Institute Inc, Cary, NC; v9 or later) will be used for the generation of all tables, listings, and statistical analyses.

Interim analyses will not be conducted due to early termination.

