7.2. Analysis of the Primary Efficacy Parameter

7.2.1. Primary Efficacy Analysis

The primary endpoint of the study is ORR in Cohort A. Objective response rate is defined as the proportion of participants who achieve a CR or PR based on RECIST v1.1 ([Eisenhauer 2009](#)), as assessed by an ICR review committee. Confirmation of CR and PR is required and documented in the ICR charter. This analysis will be based on the FAS. Participants who do not have sufficient baseline or on-study response assessment information to be adequately assessed for response status will be included in the denominators in the calculation of ORR. The 95% CI for the ORR will be estimated using the Clopper-Pearson method.

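### The above-95% chance of success in Protocol 10.1 is right for a fixed Cohort A of about 100 (exact 99.2%) but leaves out the Section 10.5 futility look; with that rule always followed at 25 it is about 92%

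*Protocol*

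**What the plan says.** Protocol 10.1 assumes an ORR of 40% and states that a sample of about 100 "would provide about > 95% probability to have a 95% CI with lower limit of > 20" percent. SAP 3.3 repeats the figure. Protocol 10.4.1 fixes the interval as Clopper-Pearson and 10.3 fixes the level at 95%.

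Protocol 10.5 adds an interim look: "A futility analysis will be performed when approximately 25 participants are enrolled into Cohort A" and meet its assessment conditions. Cohort A may then be stopped at 6 or fewer responders in the RECIST evaluable population. At that boundary the section gives a chance below 15% of still concluding at the end that ORR exceeds 20%. It closes with "This rule is just a guidance and nonbinding".

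Neither 10.1 nor 10.5 says how often a drug with the assumed 40% ORR would meet the boundary, or what the look does to the probability in 10.1.

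The SAP later drops the look: "Interim analyses will not be conducted due to early termination" (SAP 5.1; also SAP 9 and 10.1). SAP 10.1 records fewer than 10 participants at termination.

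**The concern.** A reader of 10.1 will take the chance of success for a 40%-ORR drug to be above 95% under the protocol as written. The protocol as written includes a look that can end Cohort A early, and any futility stop lowers the chance of success. Leaving a nonbinding rule out is conservative for a false-positive rate but optimistic for a probability of success.

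The below-15% figure in 10.5 does not show this cost. It describes the outlook after a poor interim result, not how often a drug that performs as assumed produces one. At stake is an undisclosed chance of stopping a drug that meets the design assumption, and a stated probability that may not hold if the protocol's own guidance is followed.

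**Working it through.** **Inputs.** True ORR 0.40, final Cohort A of 100 and success defined as a lower limit above 20% (Protocol 10.1); two-sided 95% Clopper-Pearson interval (10.3, 10.4.1); look at 25 with cut 6 (10.5). Participants who cannot be assessed stay in the denominator (10.4.1), so no dropout adjustment is needed.

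**Assumptions.** (a) The interim participants are among the final 100. Table 13 supports this: "The RECIST evaluable population includes all participants in full analysis set" who meet its assessment conditions. (b) Their responder status does not change after the look. Step 6 relaxes (b).

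**1. Critical count.** The lower limit is 19.48% at 28/100 and 20.36% at 29/100, so success needs at least 29 responders.

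**2. The plan's figure, fixed sample.** P(Bin(100, 0.40) ≥ 29) = 0.9916. The stated figure is reproduced.

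**3. Effect of the look at 25, rule always followed.**
- P(stop) = P(Bin(25, 0.40) ≤ 6) = 0.0736.
- P(continue and succeed) = Σ over x = 7 to 25 of P(Bin(25, 0.40) = x) × P(Bin(75, 0.40) ≥ 29 − x) = 0.9219. Two million simulated trials gave 0.9217.
- Loss = 0.9916 − 0.9219 = 0.0697.
- Given that the look is passed: 0.9219 / (1 − 0.0736) = 0.9951.
- Share of stopped trials that would have succeeded if continued: 0.0697 / 0.0736 = 94.7%.

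**4. Rule followed only sometimes.** If it is acted on with probability q whenever the boundary is met, whatever the count from 0 to 6, the chance of success is 0.9916 − 0.0697q. This equals 0.95 at q = 0.0416 / 0.0697 = 0.597.

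**5. Sensitivity to the two approximate sizes.** Final sample 100, cut kept at 6:

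| Look at | Always followed | Below 95% if acted on more than |
|---|---|---|
| 24 | 0.9000 | about 45% |
| 25 | 0.9219 | about 60% |
| 26 | 0.9391 | about 79% |
| 27 | 0.9525 | never below |

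Look at 25, other final sizes:

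| Final N | Responders needed | Never followed | Always followed |
|---|---|---|---|
| 90 | 27 | 0.9810 | 0.9155 |
| 95 | 28 | 0.9873 | 0.9194 |
| 105 | 30 | 0.9944 | 0.9235 |
| 110 | 31 | 0.9963 | 0.9246 |

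**6. Responder status that changes after the look.** Later scans can add first responses. Confirmation can remove some: Protocol 8.2.1 says "For participants showing a response, a confirmatory scan may be performed a minimum of 4 weeks" after the previous scan, while SAP 7.2.1 says "Confirmation of CR and PR is required and documented in the ICR charter". The documents give no rates, so the values below are assumed. The rule is always followed at 25 and the final ORR is 40%.
- Late responses: if a fraction s of eventual responders is seen by the look, X ~ Bin(25, 0.4s), and later responses among the other 25 − X have probability 0.4(1 − s)/(1 − 0.4s). s = 0.95 gives 0.8900; s = 0.90 gives 0.8484.
- Responses later not confirmed: interim rate r, each response retained with probability 0.4/r. r = 0.42 gives 0.9450; r = 0.44 gives 0.9614.

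**7. The below-15% figure in 10.5.** With 6 responders in 25, success needs 23 of the remaining 75. At a future rate of 24% (6/25) the chance is 0.1136; at the 40% assumed in 10.1 it is 0.9633. The 10.5 statement therefore fits a rate near the observed one, not the rate behind 10.1.

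**The case against.** The strongest reply is that 10.1 contains no error. It says what a sample of about 100 would provide, and that is true at 100, at 90 and at 110, and also given that Cohort A passes the look. The rule is expressly nonbinding, so quoting the fixed-sample probability is defensible. All of this stands: the point is an omission, not a miscalculation.

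The crossing of 95% is also fragile. A look at 27 with the same cut gives 0.9525. A sponsor who continued at exactly 6 responders and stopped only at 5 or fewer would have 0.9645 at a look of 25. The assumed changes in responder status move the figure from about 85% to about 96%. This also stands, and it is why 92% should be presented as one conditional case with its assumptions stated. It does not remove the omission, because 10.5 commits to performing the look and no section gives its cost.

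Finally, the look was cancelled and fewer than 10 participants were enrolled, so no estimate or confidence interval is affected. That is correct and limits the point to the record of the design.

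**Conclusion.** The concern holds. The 10.1 figure is valid without the futility stop (99.2%) but does not say that the stop is left out. With a look at exactly 25, a final Cohort A of 100, interim participants counted in the final 100 and responder status unchanged, the chance of success lies between about 92% (rule always followed) and about 99% (never followed). Always following the rule raises the chance of failure at a 40% ORR from 0.8% to 7.8%.

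One separate editorial matter carries no weight here. SAP 3.3 says "Approximately 125 participants with select FGFR alterations are planned for the final analysis of the primary endpoint of ORR", but the primary endpoint is ORR in Cohort A, about 100 participants. The same SAP section computes with about 100, so nothing would be analysed on 125.

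**What to change.** In Protocol 10.1, state that the probability is about 99% without the futility stop and about 92% if the Section 10.5 rule is followed at 25 participants, assuming that interim responder status does not change. Leave the futility cut as it is. Do not add the 92% to SAP 3.3, because the SAP no longer has an interim look.

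Editorially, SAP 3.3 should say that about 125 participants are planned in total and that the primary endpoint uses the roughly 100 in Cohort A.

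The cost is wording: no change to the cut, the sample size or any analysis. A protocol amendment would carry the approval steps in Protocol 11.1. The stated figure also becomes less favourable for the case in which the rule is followed.

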### 10.2. Populations for Analyses

[Table 13](#) presents the populations for analysis.

**Table 13: Populations for Analysis**

Population	Description
Full analysis set	
The full analysis set includes all enrolled participants who received at least 1 dose of pemigatinib.
 
The full analysis set will be used for the summary of demographics, baseline characteristics, participants disposition, and analyses of all efficacy data,

Safety	
The safety population includes all enrolled participants who received at least 1 dose of pemigatinib.
 
All safety analyses will be conducted using the safety population.

Per protocol	Participants in the full analysis set who are considered to be sufficiently compliant with the Protocol comprise the per protocol population.
RECIST evaluable	The RECIST evaluable population includes all participants in full analysis set who have at least 2 objective tumor response assessments per ICR review or who withdrew from the study or discontinued treatment without post-treatment tumor assessments.

### 10.3. Level of Significance

All CIs will be provided at a 95% confidence level.

### 10.4. Statistical Analyses

#### 10.4.1. Primary Analysis

The primary endpoint of the study is ORR in Cohort A, defined as the proportion of participants who achieve a CR or PR based RECIST v1.1 as assessed by an ICR review. The primary analysis of ORR will be based on the full analysis set. Participants who do not have sufficient baseline or on-study response assessment information to be adequately assessed for response status will be included in the denominators in the calculation of ORR. The 95% CI for the ORR will be estimated using the Clopper-Pearson method.

The ORR will also be analyzed based on the per protocol population as sensitivity analysis.

#### **10.4.2. Secondary Analysis**

Secondary efficacy analysis will be conducted for the full analysis set.

Objective response rate in Cohort B is defined as the proportion of participants who achieve a CR or a PR based RECIST v1.1 as assessed by an ICR review. Participants who do not have sufficient baseline or on-study response assessment information to be adequately assessed for response status will be included in the denominators in the calculation of ORR. The 95% CI for the ORR will be estimated using the Clopper-Pearson method.

Progression-free survival is defined as the time from the date of first dose of pemigatinib to the date of the first documented progressive disease or death due to any cause, whichever is first. Progressive disease will be evaluated according to RECIST v1.1 and assessed by an ICR review. Participants who are alive without progression before the analysis cut-off date will be censored. Censoring for PFS will follow the algorithm based on FDA guidance ([FDA 2007](#)). Progression-free survival data will be analyzed by the Kaplan-Meier method.

For objective responders, DOR is defined as the time from the date that a participant first achieves CR or PR, until the date of first documented progressive disease or death, whichever is first. Responses and progressive disease will be evaluated based on RECIST v1.1 by an ICR review. Participants who are alive without progression before analysis cut-off date will be censored. Censoring of DOR will follow the same algorithm as the censoring of PFS. Duration of response data will be analyzed by the Kaplan-Meier method.

Overall survival is defined as the time from the date of first dose of pemigatinib to the date of death due to any cause. Participants without death observed at the time of the analysis will be censored at last date known to be alive. Overall survival will be analyzed by the Kaplan-Meier method.

#### **10.4.3. Safety Analyses**

Safety analyses will be conducted for the safety population. Adverse events will be coded by the MedDRA dictionary, and TEAEs (ie, AEs reported for the first time or worsening of a pre-existing event after first dose of pemigatinib and within 30 days of last dose of pemigatinib) will be tabulated by preferred term and system organ class for all events, related events, and events of Grade 3 or higher according to NCI CTCAE v5.0, and events leading to dose interruption, dose reduction, and study treatment discontinuation. Quantitative safety variables (eg, laboratory values, vital signs) and their changes from baseline will be summarized with descriptive statistics. Clinically notable abnormal values will be flagged and tabulated based on predefined criteria.

The clinical laboratory data will be analyzed using summary statistics. In addition, distributions of key laboratory parameters may be plotted over time; these values will also be classified into CTCAE v5.0 toxicity grades, and tabulated.

Descriptive statistics and mean change from baseline will be determined for vital signs and each ECG parameter at each assessment time. Vital sign and ECG results will be reviewed for clinically notable abnormalities. Participants exhibiting clinically notable ECG abnormalities will be listed.

Measures of exposure of pemigatinib will be summarized by means of summary statistics.

## **10.5. Interim Analysis**

A futility analysis will be performed when approximately 25 participants are enrolled into Cohort A and have at least 2 objective tumor response assessments per ICR review or are withdrawn from the study or discontinued from treatment without post-treatment tumor assessments. Cohort A can be stopped for futility if  $\leq 6$  responders are observed in the RECIST evaluable population, for which there is  $< 15\%$  probability of claiming ORR  $> 20\%$  at final analysis. This rule is just a guidance and nonbinding.

## **11. SUPPORTING DOCUMENTATION AND OPERATIONAL CONSIDERATIONS**

### **11.1. Investigator Responsibilities**

- The Protocol, Protocol amendments, ICF, IB, and other relevant documents (eg, advertisements) must be submitted to an IRB/IEC by the investigator and reviewed and approved by the IRB/IEC and Health Authorities, before the study is initiated.
- The investigator is responsible for ensuring that the safety reports provided by the sponsor are reviewed and processed in accordance with regulatory requirements, the policies and procedures established by the IRB/IEC, and institutional requirements.
- Any amendments to the Protocol will require approval from both Health Authorities and IRB/IEC before implementation of changes made to the study design, except for changes necessary to eliminate an immediate hazard to study participants.
- The investigator will be responsible for the following:
  - Providing written summaries of the status of the study to the IRB/IEC annually or more frequently in accordance with the requirements, policies, and procedures established by the IRB/IEC.
  - Notifying the IRB/IEC of SAEs or other significant safety findings as required by IRB/IEC procedures.
  - Providing oversight of the conduct of the study at the site and adherence to GCP, IRB/IEC requirements, institutional requirements, and applicable laws and country-specific regulations.
- Adhering to the Protocol as described in this document and agreeing that changes to the Protocol procedures, with the exception of medical emergencies, must be discussed and approved, first, by the sponsor or its designee and, second, by the IRB/IEC. Each investigator is responsible for enrolling participants who have met the specified eligibility criteria.
- Retaining records in accordance with all local, national, and regulatory laws but for a minimum period of at least 2 years after the last marketing application approval in an ICH region and until there are no pending or contemplated marketing applications in an ICH region, or if not approved, 2 years after the termination of the test article for investigation to ensure the availability of study documentation should it become necessary for the sponsor or a regulatory authority to review.
  - The investigator must not destroy any records associated with the study without receiving approval from the sponsor. The investigator must notify the sponsor or its designee in the event of accidental loss or destruction of any study records. If the investigator leaves the institution where the study was conducted, the sponsor or its designee must be contacted to arrange alternative record storage options.

- All eCRF data entered by the site (including audit trail), as well as computer hardware and software (for accessing the data), will be maintained or made available at the site in compliance with applicable record retention regulations. The sponsor will retain the original eCRF data and audit trail.

